7.1.2.6.7 Disease Progression Assessments

After the first documentation of progression it is at the discretion of the investigator to keep a clinically stable subject on trial treatment or to stop trial treatment until repeat imaging performed 4-6 weeks later confirms progression. Clinical Stability may be defined as:

- 1) Absence of symptoms and signs indicating clinical significant progression of disease (including worsening of laboratory values) indicating disease progression.
- 2) No decline in ECOG performance status.
- 3) Absence of rapid progression of disease or progressive tumor at critical anatomical sites (eg, cord compression) requiring urgent alternative medical intervention.

Subjects that are deemed clinically unstable are not required to have repeat imaging for confirmation. If progression is confirmed, then the subject will be discontinued from trial treatment. If progression is not confirmed, then the subject should resume/continue trial treatment provided:

- The sponsor is consulted and provides approval to continue treatment
- No other anti-tumor therapy (eg, chemotherapy, radiation, etc.) has been administered

Patients should have their next scan according to the every 12-week schedule from first dose of study treatment, which would be approximately 12 weeks from the date of the scan that first showed progression. When feasible, subjects should not be discontinued until progression is confirmed.

7.1.2.6.8 Biopsy Collection and Correlative Studies Blood Collection

All subjects enrolled into this study must be able to provide an archived FFPE biopsy sample or newly obtained core or excisional biopsy (FNA not adequate) to be submitted for

characterization at a central lab. Submission of formalin-fixed paraffin embedded tumor tissue sample blocks are preferred; if submitting unstained slides, the slides should be freshly cut and submitted to the testing laboratory within 14 days from site slide sectioning date otherwise a new specimen will be requested.

Biopsy sites should be selected so that subsequent biopsies can be performed at the same location. Tumors that are inaccessible or contraindicated due to subject safety concerns are exempt from this requirement.

Bone marrow and lymph node biopsies will be collected as per [Table 7](#) below.

Table 7 Bone Marrow and Lymph Node Biopsy Assessments

Indication	Timing of Biopsy
Cohorts 1, 2 and 3: Lymph Node Biopsy (Lymph node biopsy)	Screening biopsy (archival or new) is required. Biopsy at Wk. 12 (\pm 7 days) and at the time of discontinuation due to progression is optional but highly recommended.
Cohorts 1, 2 and 3: Bone marrow biopsy/aspirate (All subjects will have bone marrow biopsy/aspirate performed at Screening. Subsequent bone marrow assessments will only be performed in subjects who have bone marrow involvement.)	Screening, to confirm CR (if subject has bone marrow involvement), and as clinically indicated.

Blood for correlative biomarker studies should be collected as per [Table 8](#) below.

Table 8 Blood for Correlative Studies

Cohorts	Timing of Correlative Blood Collection
Cohorts 1, 2, and 3	Whole Blood for RNA/DNA : Screening, pre-dose on Cycle 2 Day 1, Wk. 12 assessment, and upon progression.
Cohorts 1, 2, and 3	Whole Blood for Immunophenotyping : pre-dose on Cycles 1, 2, 3 and pre-dose on Wk. 12 assessment.
Cohorts 1, 2, and 3	Plasma for Nanostring : Screening and Wk. 12 assessment

7.1.2.7 Patient Reported Outcomes (PROs)

The EuroQol EQ-5D and EORTC QLQ-C30 questionnaires will be administered by trained site personnel and completed electronically by the subjects themselves. It is strongly recommended that all electronic PROs (ePROs) are administered prior to drug administration, adverse event evaluation and disease status notification. The ePROs are completed in the following order: EuroQol EQ-5D first, then EORTC QLQ-C30 at the time points specified in the Trial Flow Charts.

7.1.3 Laboratory Procedures/Assessments

Details regarding specific laboratory procedures/assessments to be performed in this trial are provided below.

7.1.3.1 Laboratory Safety Evaluations (Hematology, Chemistry, and Urinalysis)

Laboratory tests for hematology, chemistry, and urinalysis are specified in [Table 9](#).

Table 9 Laboratory Tests

Hematology	Chemistry	Urinalysis	Other
Hematocrit	Albumin	Blood	Serum β -human chorionic gonadotropin (β -hCG)
Hemoglobin	Alkaline phosphatase	Glucose	PT (INR)
CBC with differential	Alanine aminotransferase (ALT)	Protein	aPTT
Platelet count	Aspartate aminotransferase (AST)	Specific gravity	Total Triiodothyronine (T3) (or FT3)
WBC (total and differential)	Lactate dehydrogenase (LDH)	Microscopic exam, if abnormal results are noted	Free thyroxine (T4)
Red Blood Cell Count	Carbon Dioxide (CO_2 or bicarbonate) ^a	Urine pregnancy test	Thyroid stimulating hormone (TSH)
Absolute Neutrophil Count	Creatinine		Anti-pembrolizumab Antibodies
Absolute Lymphocyte Count	Uric Acid		PK
	Calcium		Blood for FBR
	Chloride		Blood for correlative studies
	Glucose		
	Phosphorus		
	Potassium		
	Sodium		
	Magnesium		
	Total Bilirubin		
	Direct and Indirect Bilirubin, if total bilirubin is elevated above the upper limit of normal		
	Total protein		
	Blood Urea Nitrogen ^b		

^a If considered standard of care in your region. If these tests are not done as part of standard of care in your region then these tests do not need to be performed

^b Blood Urea Nitrogen is preferred; if not available Urea may be tested.

Laboratory tests for screening or entry into the Second Course Phase should be performed within 7 days prior to the first dose of treatment. After Cycle 1, pre-dose laboratory procedures can be conducted up to 72 hours prior to dosing. Results must be reviewed by the investigator or qualified designee and found to be acceptable prior to each dose of trial treatment.

7.1.3.2 Pharmacokinetic/Pharmacodynamic Evaluations

7.1.3.2.1 Pharmacokinetic Evaluations

To further evaluate pembrolizumab immunogenicity and pembrolizumab exposure in this indication, and also to evaluate exposure of the proposed dosing regimen, sample collections for analysis of anti-drug antibodies (ADA) and PK are currently planned as shown in the Trial Flowchart (Sections 6.1. and 6.2). Blood samples will be obtained to measure pharmacokinetics of serum pembrolizumab monotherapy. The pembrolizumab serum maximum concentration (C_{max}) and minimum concentration (C_{trough}) at planned visits and times will be summarized. If ongoing ADA and/or PK results continue to be consistent with existing ADA and/or PK data from other pembrolizumab clinical trials, it may be decided to discontinue or reduce further sample collection in this study.

Pharmacokinetic data will also be analyzed using nonlinear mixed effects modeling. Based on pharmacokinetic (PK) data obtained in this study as well as PK data obtained from other studies (if available), a population PK analysis will be performed to characterize pharmacokinetic parameters (Clearance (CL), Volume of distribution (V) and evaluate the effect of extrinsic and intrinsic factors to support proposed dosing regimen. Pharmacokinetic data will also be used to explore the exposure-response relationships for pembrolizumab antitumor activity/efficacy as well as safety in the proposed patient population, if feasible. The results of these analyses, if performed, will be reported separately.

Blood Collection for Serum MK-3475 Sample collection, storage and shipment instructions for serum samples will be provided in the procedure manual. PK samples should be drawn according to the PK collection schedule for subjects who receive pembrolizumab (MK-3475). Every effort should be taken to collect samples at 30 days (+/- 3 days) and 3 months (+/- 3 days) after end of pembrolizumab treatment.

7.1.3.2.2 Blood Collection for Anti-pembrolizumab Antibodies MK-3475

Sample collection, storage and shipment instructions for serum samples will be provided in the procedure manual. Anti- pembrolizumab antibody samples should be drawn according to the ADA collection schedule for subjects who receive pembrolizumab (MK-3475). Every effort should be taken to collect samples at 30 days and 3 months after end of pembrolizumab treatment for ADA. Simultaneous PK sampling is required for interpretation of ADA analysis.

7.1.3.3 Future Biomedical Research

The following specimens are to be obtained as part of Future Biomedical Research:

- Leftover DNA for future use
- Leftover Bone Marrow Biopsy/Aspirate samples
- Leftover Lymph node biopsies
- Leftover Correlative blood samples

7.1.4 Other Procedures

7.1.4.1 Withdrawal/Discontinuation

Subjects who discontinue/withdraw from treatment prior to completion of the treatment regimen should be encouraged to continue to be followed for all remaining study visits.

When a subject discontinues/withdraws from participation in the trial, all applicable activities scheduled for the final trial visit should be performed at the time of discontinuation. Any adverse events which are present at the time of discontinuation/withdrawal should be followed in accordance with the safety requirements outlined in Section 7.2 - Assessing and Recording Adverse Events. Subjects who attain a CR may discontinue treatment with the option of restarting treatment if they meet the criteria specified in Section 7.1.5.2.2. After discontinuing treatment following assessment of CR, these subjects should return to the site for a Safety Follow-up Visit (described in Section 7.1.5.3.1) and then proceed to the Follow-Up Period of the study (described in Section 7.1.5.4).

7.1.4.1.1 Withdrawal From Future Biomedical Research

Subjects may withdraw their consent for Future Biomedical Research and have their specimens and all derivatives destroyed. Subjects may withdraw consent at any time by contacting the principal investigator for the main trial. If medical records for the main trial are still available, the investigator will contact the Sponsor using the designated mailbox **CCI** [REDACTED] and a form will be provided by the Sponsor to obtain appropriate information to complete specimen withdrawal. Subsequently, the subject's specimens will be removed from the biorepository and be destroyed. A letter will be sent from the Sponsor to the investigator confirming the destruction. It is the responsibility of the investigator to inform the subject of completion of destruction. Any analyses in progress at the time of request for destruction or already performed prior to the request being received by the Sponsor will continue to be used as part of the overall research trial data and results. No new analyses would be generated after the request is received.

In the event that the medical records for the main trial are no longer available (e.g., if the investigator is no longer required by regulatory authorities to retain the main trial records) or the specimens have been completely anonymized, there will no longer be a link between the subject's personal information and their specimens. In this situation, the request for specimen destruction cannot be processed.

7.1.4.2 Blinding/Unblinding

This is an open label trial; there is no blinding for this trial.

7.1.4.3 Calibration of Critical Equipment

The investigator or qualified designee has the responsibility to ensure that any critical device or instrument used for a clinical evaluation/test during a clinical trial that provides important information about inclusion/exclusion criteria and/or safety or efficacy parameters shall be

suitably calibrated and maintained to ensure that the data obtained is reliable and/or reproducible. Documentation of equipment calibration must be retained as source documentation at the trial site.

Critical Equipment for this trial includes:

- Laboratory equipment- as required for inclusion labs and trial assessments
- Imaging equipment- as required for trial objectives
- Infusion equipment- as required for administering drug product

See protocol-specified guidance in the Administrative Binder, Pharmacy Manual and Site Imaging Manual.

7.1.5 Visit Requirements

Visit requirements are outlined in Section 6.0 - Trial Flow Chart. Specific procedure-related details are provided above in Section 7.1 - Trial Procedures.

7.1.5.1 Screening

Approximately 28 days prior to randomization, potential subjects will be evaluated to determine that they fulfill the entry requirements as set forth in Section 5.1. Screening procedures may be repeated after consultation with the Sponsor. Visit Requirements are outlined in Section 6.0.

Written consent for the main study must be obtained prior to performing any protocol specific procedure. Results of a test performed prior to the subject signing consent as part of routine clinical management are acceptable in lieu of a screening test if performed within the specified time frame. Screening procedures are to be completed within 28 days prior to the first dose of trial treatment except for the following:

- Laboratory tests are to be performed within 7 days prior to the first dose of trial treatment.
- For women of reproductive potential, a urine pregnancy test will be performed within 72 hours prior to the first dose of trial treatment. If urine pregnancy results cannot be confirmed as negative, a serum pregnancy test will be required (performed by the local study site laboratory).
- When an archival biopsy is being used for PD-L1 characterization, it is not required to be obtained within 28 days prior to the first dose of trial treatment.

Subjects may be rescreened after initially failing to meet the inclusion/exclusion criteria. Results from assessments performed during the initial screening period are acceptable in lieu

of a repeat screening test if performed within the specified time frame and the inclusion/exclusion criteria is met.

7.1.5.2 Treatment Period

Visit requirements are outlined in Section 6.0 – Trial Flow Chart. Specific procedure-related details are provided above in Section 7.1 – Trial Procedures. Subjects who have not progressed may receive up to 35 cycles (approximately 2 years) of pembrolizumab during treatment period.

7.1.5.2.1 Subjects Who Continue Treatment Beyond Disease Progression

Subjects that continue treatment with pembrolizumab after documented disease progression (Section 7.1.5.2.2), must follow the same visit requirements as outlined in Section 6.2 Study Flow Chart.

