3.3 Exploratory Objectives

Within each of, and potentially pooled over, the 3 cohorts of subjects with R/R cHL:

(1) **Objective:** To evaluate ORR, CRR, PFS and DOR for subjects who continue treatment with pembrolizumab beyond documented progression (see Section 8.6.1).

(2) **Objective:** To explore the PK profile of pembrolizumab (see Section 7.1.3.2.1)

- (3) **Objective:** To evaluate changes in health-related quality-of-life assessments from baseline using the EORTC QLQ-C30 and EuroQol EQ-5D (see Section 4.2.3.2.1.2)
- (4) **Objective:** To further evaluate pembrolizumab immunogenicity and exposure of the proposed dose and dosing regimen (see Section 4.2.3.3).
- (5) **Objective:** To compare the extent of pre-pembrolizumab PD-L1 expression in tumor biopsies for pembrolizumab responders versus non-responders (see Section 4.2.3.2.1.1)
- (6) **Objective:** To investigate the relationship between candidate efficacy biomarkers and anti-tumor activity of pembrolizumab utilizing pre- and post-treatment lymph node biopsies and blood sampling (see Section 4.2.3.4).
- (7) **Objective:** To explore the relationship between genetic variation and response to the treatment(s) administered. Variation across the human genome will be analyzed for association with clinical data collected in this study (See Section 4.2.3.4).

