5.8 Subject Withdrawal/Discontinuation Criteria

Subjects may withdraw consent at any time for any reason or be dropped from the trial at the discretion of the investigator should any untoward effect occur. In addition, a subject may be withdrawn by the investigator or the Sponsor if enrollment into the trial is inappropriate, the trial plan is violated, or for administrative and/or other safety reasons. Specific details regarding discontinuation or withdrawal procedures; including specific details regarding withdrawal from Future Biomedical Research, are provided in Section 7.1.4 – Other Procedures.

A subject must be discontinued from the trial for any of the following reasons:

- The subject or legal representative (such as a parent or legal guardian) withdraws consent.

A subject must be discontinued from treatment (but may continue to be monitored in the trial) for any of the following reasons:

- The subject or legal representative (such as a parent or legal guardian) withdraws consent for treatment
- Documented disease progression Note: Subjects may continue to receive trial treatment beyond progression if the subject meets the criteria outlined in Section 7.1.2.6.7.
- Unacceptable adverse experiences as described in Section 5.2.1.2, 5.6.1, and 7.2
- Intercurrent illness that prevents further administration of treatment
- Investigator's decision to withdraw the subject
- The subject has a confirmed positive serum pregnancy test
- Noncompliance with trial treatment or procedure requirements
- The subject is lost to follow-up
- Administrative reasons

The End of Treatment and Follow-up visit procedures are listed in Section 6 (Flow Chart) and Section 7.1.5 (Visit Requirements). After the end of treatment, each subject will be followed for 30 days for adverse event monitoring (serious adverse events will be collected for 90 days after the end of treatment as described in Section 7.2.3.1). Subjects who discontinue for reasons other than progressive disease will have post-treatment follow-up for disease status until disease progression, initiating a non-study cancer treatment, withdrawing consent or becoming lost to follow-up. After documented disease progression or the start of new antineoplastic therapy each subject will be followed for overall survival until death, withdrawal of consent, or the end of the study, whichever occurs first.

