- m. Treatment response assessment is based upon the IWG response criteria (Cheson 2007). “Diagnostic quality” CT and PET scans should be performed at Screening (within 28 days prior to first dose of trial treatment). If PET or CT scan at Screening is positive for disease of the neck, subsequent CT scans must include the neck. If CT and PET scans at Screening are negative for disease in the neck, subsequent CT scans may omit the neck. Following screening, CT scans should be repeated every 12 weeks for subsequent assessments. PET should be repeated at Week 12, Week 24, to confirm CR, and as clinically indicated. PET may provide additional information when progression is suspected, and can be obtained at the investigator’s discretion. Response assessments should occur at Wk. 12, and every 12 weeks (+/- 7 days) following the Wk. 12 assessment. Imaging timing should follow calendar days and should not be adjusted for delays in cycle starts or extension of pembrolizumab cycle frequencies. For subjects who discontinue for reasons other than PD, assessments should continue until the subject has documented PD. The first assessment may be performed earlier than 12 weeks if in the opinion of the investigator the patient is clinically progressing. During the follow up period, the imaging schedule should proceed every 12 weeks from the day of the last imaging performed before subject enters the follow up period. Assessment of lymphoma B symptoms should occur with each disease response assessment. Bone marrow assessment is required to document CR, if the bone marrow was involved at screening.
- n. If subjects have stable disease, partial response, or complete response a repeat CT scan is not required for confirmation, they should continue on the every 12 week assessment schedule. In the setting where a subject assessment shows PD at the Week 12 disease response assessment study drug may be continued, at the discretion of the PI, until the next disease response assessment provided that the subjects’ clinical condition is stable. However, imaging should occur at any time where there is clinical suspicion of progression
- o. In subjects with PD at Wk. 12, who continued study therapy beyond week 12 a radiological assessment should be performed at the time of treatment discontinuation. If previous scan was obtained within 4 weeks prior to the date of discontinuation, then a repeat scan at treatment discontinuation isn’t mandatory.

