- aa. Tumor biopsies are required for subjects at Screening. At Screening an archival biopsy may be used, if an archival biopsy is not available a new biopsy must be obtained. Tumor biopsies **may** be obtained at Wk. 12 (\pm 7 days). A biopsy is also **highly recommended** at time of discontinuation due to progression, but is not required. Biopsy of lesions on study should be limited to non-target lesions or new lesions if their pathologic etiology is ambiguous and the tissue sample should have proper size to enable multiple planned biomarker analyses, but not artificially decrease the longest diameter of the lesion. If a tumor biopsy was of a target lesion during eligibility assessment, it is preferred to obtain a new baseline scan.
- bb. Whole blood for Correlative Study samples (RNA/DNA) should be collected at Screening, pre-dose on Cycle 2 Day 1, at the time of the Wk. 12 disease response assessment, and upon progression. See Procedures Manual. Any leftover samples from the correlative blood studies will be stored for future biomedical research if the subject signs the FBR Consent.
- cc. Whole Blood for Correlative Study samples (Immunophenotyping) should be collected pre-dose on Cycle 1, Cycle 2, Cycle 3 and pre-dose at the time of the Wk. 12 disease response assessment. Cycle 5. See Procedures Manual. Any leftover samples from the correlative blood studies will be stored for future biomedical research if the subject signs the FBR Consent.
- dd. Plasma and Serum biomarker samples should only be collected at Screening.
- ee. Plasma for Correlative Studies (Nanostring) should be collected at Screening and post-dose on Wk. 12. See Procedures Manual. Any leftover samples from the correlative blood studies will be stored for future biomedical research if the subject signs the FBR Consent.
- ff. For Both PK and anti-pembrolizumab antibody: Pre-dose trough PK and anti-pembrolizumab antibody samples will be collected at Cycles 1, 2, 4, 6, 8 and every 4 cycles thereafter (eg, Cycle 12, Cycle 16, Cycle 20, etc.), 30 days after discontinuation of study drug and 3 months after discontinuation of study drug (or until the subject starts new anti-cancer therapy). All pre-dose trough samples should be drawn within 24 hours before infusion of pembrolizumab (-24 to 0 hrs. window at Cycle 1; -48 to 0 hrs. window at subsequent visits is allowed).

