- gg. For PK sample collection only: Additional post-dose peak PK samples will be drawn within 30 minutes (0 – 45 minutes) after end of pembrolizumab infusion at Cycles 1 and 8. An additional single PK sample should be drawn at 24 hours (20 – 28 hours) (Day 2), between 72 and 168 hours (48 – 192 hours) (Day 4-8), and 336 hours (288 – 384 hours) (Day 15) after Cycle 1 dosing.
- hh. This sample should be drawn for planned genetic analysis of DNA and drug response unless there is either a documented law or regulation prohibiting collection, or unless the IRB/IEC does not approve of the collection of the sample for these purposes. If the sample is collected, any leftover extracted DNA will be stored for future biomedical research if the subject signs the FBR consent.
- ii. Patient reported outcomes (PROs) are assessed every cycle for the first five cycles and every 12 weeks thereafter until PD while the subject is receiving study treatment. PROs will also be obtained at the Treatment Discontinuation Visit and 30-day Safety Follow-up Visit. If the Treatment Discontinuation Visit occurs 30 days from the last dose of study treatment, at the time of the mandatory Safety Follow up Visit, PROs do not need to be repeated. PROs are to be administered by trained site personnel and completed electronically by subjects. It is strongly recommended that all electronic PROs (ePROs) are administered prior to drug administration, adverse event evaluation and disease status notification. The PROs should be administered in the following order: EQ-5D followed by EORTC QLQ-C30.

6.2 Study Flow Chart: Cohorts 1, 2, and 3: Second Course Phase (Retreatment for Post-Complete Response Relapse Only)

Trial Period:	Treatment Cycles ^a									End of Treatment	Post-treatment		
	1	2	3	4	To be repeated beyond 9 cycles								
Treatment Cycle/Title:	1	2	3	4	5	6	7	8	9	Discon	Post-Treatment Safety Follow-up	Follow-up Visits ^b	Survival Follow-up ^c
Scheduling Window (Days) ^d	+ 3	± 3	± 3	± 3	± 3	± 3	± 3	± 3	± 3	At time of Discon	30 days post Last Infusion (±3 days)	Every 12 weeks (±7 days)	Every 12 weeks (±14 days)
Administrative Procedures													
Eligibility Criteria ^e	X												
Prior and Concomitant Medication Review ^f	X	X	X	X	X	X	X	X	X	X			
Pembrolizumab Administration ^a	X	X	X	X	X	X	X	X	X				
Post-study anticancer therapy status												X	X
Survival Status ^e	↔												X
Clinical Procedures/Assessments													
Review Adverse Events ^g	X	X	X	X	X	X	X	X	X	X ^h		X	

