7.1.5.2.2 Second Course Phase (Retreatment Period for Post-complete Remission Relapse ONLY)

Subjects may be eligible to receive up to an additional 17 cycles (approximately 1 year) of pembrolizumab in the Retreatment Period of this study if the study remains open and the subject meets all of the following conditions:

- Stopped (or completed) initial treatment with pembrolizumab after attaining an confirmed CR by investigator assessment according to respective response criteria
- Was treated for at least 24 weeks (8 cycles) with pembrolizumab before discontinuing therapy
- Received at least two treatments with pembrolizumab beyond the date when the initial CR was declared
- Experienced an investigator-determined confirmed disease progression after stopping their initial treatment with pembrolizumab
- Did not receive any anti-cancer treatment since the last dose of pembrolizumab
- Have a performance status of 0 or 1 on the ECOG Performance Scale
- Demonstrate adequate organ function as detailed in Section 5.1.2
- Female subject of childbearing potential should have a negative urine or serum pregnancy test within 72 hours prior to receiving retreatment with study medication.
- Female subjects of childbearing potential should be willing to use 2 methods of birth control or be surgically sterile, or abstain from heterosexual activity for the course of the study through 120 days after the last dose of study medication (Reference Section

5.7.2). Subjects of child bearing potential are those who have not been surgically sterilized or have not been free from menses for > 1 year.

Note: Abstinence is acceptable if this is the usual lifestyle and preferred contraception for the subject.

- Male subjects should agree to use an adequate method of contraception starting with the first dose of study therapy through 120 days after the last dose of study therapy.

Note: Abstinence is acceptable if this is the usual lifestyle and preferred contraception for the subject.

- Does not have a history or current evidence of any condition, therapy, or laboratory abnormality that might interfere with the subject's participation for the full duration of the trial or is not in the best interest of the subject to participate, in the opinion of the treating investigator.

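### Section 7.1.5.2.1 sends subjects treated through progression to the post-CR retreatment section and chart, which do not fit them and have no rows for several planned exploratory collections

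*Combined protocol and SAP*

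**What the plan says.** Section 7.1.5.2.1, on treatment beyond progression, opens with "Subjects that continue treatment with pembrolizumab after documented disease progression (Section 7.1.5.2.2" as its reference and then says that these subjects "must follow the same visit requirements as outlined in Section 6.2 Study Flow Chart".

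Both targets belong to another situation. Chart 6.2 is titled "Second Course Phase (Retreatment for Post-Complete Response Relapse Only". Section 7.1.5.2.2 carries the same restriction in its heading, and its first condition is "Stopped (or completed) initial treatment with pembrolizumab after attaining an confirmed CR by investigator assessment". It also requires that progression came after the subject had stopped the initial treatment.

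Other sections deal with treatment through progression differently:

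- Section 5.8: "Subjects may continue to receive trial treatment beyond progression if the subject meets the criteria outlined in Section 7.1.2.6.7".
- Chart 6.1, footnote n, allows for continuation after progression (PD) at Week 12. Footnote o adds an instruction for the same subjects: "In subjects with PD at Wk. 12, who continued study therapy beyond week 12 a radiological assessment should be performed" when treatment is discontinued.
- Section 3.3 sets an exploratory objective on ORR, CRR, PFS and DOR "for subjects who continue treatment with pembrolizumab beyond documented progression".

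On sampling, chart 6.1 footnote ff says that pre-dose PK and anti-drug antibody (ADA) "samples will be collected at Cycles 1, 2, 4, 6, 8 and every 4 cycles thereafter", then 30 days and 3 months after discontinuation. Section 7.1.3.2.1 states that PK/ADA collection is shown in both 6.1 and 6.2.

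**The concern.** The instruction is mandatory in wording, and it governs a group that the protocol expects to exist. A site that obeys it leaves chart 6.1 at first progression and moves to a chart designed for a restart at a new Cycle 1, with eligibility re-checked. That chart has no rows for questionnaires, PK, ADA, correlative blood or lymph-node biopsy. Planned data for the PK, quality-of-life, immunogenicity and biomarker objectives (Section 3.3, items 2, 3, 4 and 6) could then go uncollected. The quality-of-life analysis in Section 8.6.3.2 could also lose its assessment 30 days after discontinuation. A site that instead follows footnotes n and o of chart 6.1 would collect these data, so collection could differ between sites.

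**Working it through.** No power or error-rate figure is involved. The check compares the passages and counts scheduled collections.

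**1. Can a subject treated through a first PD satisfy the cited section?** Section 7.1.5.2.2 needs (a) treatment stopped or completed after a confirmed CR and (b) progression after stopping. A subject who progresses on treatment and continues without a break fails both. The mismatch goes beyond the title of chart 6.2: its footnote e limits restarting to subjects who attained a CR and then discontinued or finished, and its footnote k requires the 7.1.5.2.2 criteria.

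**2. What does chart 6.1 schedule after first PD, and what does chart 6.2 keep?**

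| Collection | Chart 6.1 after first PD | Chart 6.2 | Restated outside the charts |
|---|---|---|---|
| On-treatment PK/ADA troughs | Remaining cycles of 6, 8, 12, 16, ... | No row | No; 7.1.3.2.1 points to both charts |
| Cycle 8 post-dose PK peak | Once, if PD came before Cycle 8 | No row | No |
| PK/ADA at 30 days and 3 months | Up to 2; sampling ends if new anticancer therapy starts | No row | 7.1.3.2.1 and 7.1.3.2.2 |
| On-treatment questionnaires | None; footnote ii ends them at PD | No row | Not applicable |
| Questionnaires at discontinuation and 30 days | 2, or 1 if the visits coincide | No row | No; 7.1.2.7 defers to the charts, 8.6.3.2 analyses the 30-day point |
| RNA/DNA blood | 1, upon progression, placed in the discontinuation column | No row | Table 8 |
| Lymph-node biopsy | Optional, at discontinuation for progression | No row | Table 7 |
| Immunophenotyping, Nanostring plasma | None after a PD at Week 12 or later | No row | Table 8 |
| CT/PET and response assessment | Every 12 weeks | Kept | 7.1.2.6.7 |

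**3. Size of the PK/ADA part.** From footnote ff, the trough cycles within 35 cycles are 1, 2, 4, 6, 8, 12, 16, 20, 24, 28 and 32. With 3-week cycles, Weeks 12, 24 and 36 fall at Cycles 5, 9 and 13. The last treated cycle is an assumption. Time points after PD = troughs strictly after the PD cycle, up to the last cycle, plus the two post-treatment samples.

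| PD at | Last cycle | Troughs after PD | Total |
|---|---|---|---|
| 5 | 7 | 6 | 1 + 2 = 3 |
| 5 | 9 | 6, 8 | 2 + 2 = 4 |
| 5 | 35 | 6, 8, 12, 16, 20, 24, 28, 32 | 8 + 2 = 10 |
| 9 | 11 | none | 0 + 2 = 2 |
| 9 | 13 | 12 | 1 + 2 = 3 |
| 9 | 35 | 12, 16, 20, 24, 28, 32 | 6 + 2 = 8 |
| 13 | 15 | none | 0 + 2 = 2 |
| 13 | 17 | 16 | 1 + 2 = 3 |
| 13 | 35 | 16, 20, 24, 28, 32 | 5 + 2 = 7 |

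The Cycle 8 peak adds one PK sample when PD is at Cycle 5 and dosing reaches Cycle 8. Section 7.1.2.6.7 ends treatment once repeat imaging 4 to 6 weeks later confirms progression. Six weeks is two cycles, so the shortest horizon in each group, with 0 or 1 trough, is the relevant one for confirmed progressors. The Cycle 35 rows are outer bounds.

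**4. Imaging clock.** Chart 6.2 footnote k runs 12-week assessments from its own Cycle 1, with PET at its own Weeks 12 and 24. Section 7.1.2.6.7 keeps subjects whose progression is not confirmed on the 12-week schedule counted from first dose. The two anchors differ.

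**The case against.** The strongest reply is that sites have enough other text to act correctly. Footnotes n and o keep continuing subjects within chart 6.1. Tables 7 and 8 call for the progression blood and the biopsy, and Sections 7.1.3.2.1 and 7.1.3.2.2 call for the 30-day and 3-month samples whichever chart is in use. The sponsor may also reduce or stop PK/ADA sampling. This narrows the consequence. It leaves the post-PD troughs and the last two questionnaire visits resting on chart 6.1 alone, and it leaves a mandatory sentence pointing away from that chart.

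A second reply is that 7.1.5.2.1 was meant for subjects who restart after relapse, in which case its references are right and its heading is wrong. The sentence speaks of continuing, not restarting, and that reading would leave uninterrupted treatment without an entry of its own in the visit requirements. Some correction is needed either way.

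A third reply concerns timing and has force. Section 4.3 describes 210 treated subjects, from a report that the reference list dates to July 2017. First-course treatment is capped at 35 cycles (35 × 3 = 105 weeks), and the current amendment dates from December 2022. If all first courses began before that report, a correction now would recover essentially no first-course samples. Its remaining value is in the clarity of the document and in interpreting data already collected.

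**Conclusion.** The point holds as a minor internal inconsistency. The cited section and chart cannot apply to subjects who continue through a first progression, and chart 6.2 lacks rows that chart 6.1 has. Section 7.1.3.2.1 is also wrong about what 6.2 shows.

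Per affected subject, the collections resting on chart 6.1 alone are 0 to 8 PK/ADA troughs under the assumed timings, possibly one PK peak, and one or two questionnaire visits. The RNA/DNA blood, the optional biopsy and up to two post-treatment PK/ADA samples lose their chart prompt but are restated in the text. The number of affected subjects is not given, so no total can be stated.

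A reader might infer more than the documents support:

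- **That every post-progression collection is lost.** On-treatment questionnaires already end at PD under 6.1, the late biopsy is optional, and several samples are restated.
- **That imaging restarts at a new Week 0.** Section 7.1.2.6.7 says otherwise for these subjects, so this is a conflict to reconcile and not an established effect.
- **That the exploratory ORR, CRR, PFS and DOR analyses are damaged.** They need response assessments, which 6.2 keeps.
- **That informative missingness is established.** Any loss would fall on progressors only, but neither its occurrence nor its extent is shown.

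The primary ORR analysis is not affected.

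**What to change.** Reconcile Section 7.1.5.2.1 with Sections 5.8 and 7.1.2.6.7, with footnotes n and o of chart 6.1, and with the title of chart 6.2. For subjects who continue without a break, make the visit and sample schedule the 6.1 data-collection schedule, and keep 6.2 for retreatment after a post-CR relapse. State one anchor for their 12-week imaging. Reconcile the statement in Section 7.1.3.2.1 that 6.2 shows PK/ADA sampling with that chart.

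The cost is two cross-references in one sentence, one line on the imaging anchor, and one correction in 7.1.3.2.1. No dose, endpoint or hypothesis changes, and no continuation or treatment rule needs to be prescribed.

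Because most first-course data are probably already in hand, the supplemental SAP or the study report should also state how many subjects continued past progression and which chart their sites followed. It should give the number with PK/ADA and 30-day questionnaire data. That takes one short table.
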